The primary endpoint evaluates if the iLet system performs as designed, receiving CGM signals and delivering drug doses (insulin and, when applicable, glucagon) calculated by the control algorithm with an acceptable degree of reliability and accuracy. No formal test of the primary endpoint is planned.

The null hypothesis tested for the key secondary endpoint is:

The amount of hypoglycemia using the bihormonal configuration of the iLet is equal to the amount of hypoglycemia using the insulin-only configuration of the iLet.

The proportion of time with CGM glucose < 54 mg/dl across days 2-7 estimates the amount of hypoglycemia.

VII.b Sample Size Determination

No formal statistical comparisons have been done for this study. This study is primarily intended to verify that the iLet is operating as expected (based on its design and on bench testing) in each configuration in the outpatient setting. A sample size of 10 subjects in a crossover design is considered adequate for this purpose.

VII.c Populations for Analyses

Adult subjects (≥ 18 years old) with type 1 diabetes.

VII.d Statistical Analyses

VII.d.i General Approach

An intention-to-treat analysis will be performed. Descriptive statistics will be used to summarize patient characteristics and assessments. No formal testing will be conducted to establish superiority. In general, all data will be summarized with descriptive statistics for each treatment group. Unless otherwise specified, continuous data will be summarized by presenting the number of non-missing observations, mean, standard deviation (SD), median, minimum, and maximum. Categorical data will be summarized by presenting the number of patients and percentage for each category. P-values can be displayed to aid interpretation, not for inference. Tables, figures and listings of all primary, secondary and safety endpoints will be created.

Baseline and demographic data will be summarized using descriptive statistics. All comparisons will be between treatments within patients. Listings of individual patient data will be presented.

Data from periods when the bionic pancreas was not in use will be included, if available (Dexcom CGM data may not be available in some failure modes). In cases where an arm was not completed we will use the available data from that arm in the data analysis.

VII.d.ii Analysis of the Primary Efficacy Endpoint

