The primary endpoint is whether the iLet operates as designed during the study arms. An arm will be considered to have successfully met its primary endpoint if each of the following is true during the time that the iLet is powered on over the entire treatment period (days 1–7):

1. The percentage of time that valid CGM glucose readings are captured by the iLet is $\geq 80\%$. Sensor warm-up periods, occasions of failed communication between the iLet and sensor–transmitter unit, or other sensor failure conditions are all counted as times when valid CGM glucose reading are not captured.
2. The percentage of the time that each drug channel (insulin, and if applicable, glucagon) is available is $\geq 95\%$. A channel is considered to be available if a cartridge is successfully loaded, there is no pending occlusion alarm or other system failure to prevent attempting a delivery on that channel, and the cartridge is not yet considered empty.
3. The ratio of cumulative drug doses delivered to cumulative drug doses attempted is between 0.95 and 1.05, inclusive, for insulin and, if applicable, for glucagon. Attempted doses refer to calculated doses that are issued for delivery when the channel is available. Doses delivered refers to the dose amounts reported back by the motor controller after the delivery attempts are completed.

If all three evaluations hold true for a patient’s treatment period, the patient-period is operationally successful. The proportion of patients that are operationally successful will be presented by pump type.

VII.d.iii Analysis of the Secondary Endpoints

The proportion of time spent with CGMG < 54 mg/dl and the mean CGMG are analyzed using methods for paired data. The treatment means and mean difference between treatments will be estimated together with the corresponding 95% confidence interval and compared using a paired t-test for normally distributed data or Wilcoxon signed-rank test for non-normally distributed data. Time < 54 mg/dl and mean glucose will be computed from all available CGM data during days 2-7 for both study arms.

All questionnaire data for patients who have completed a minimum of 4 days with a device will be included. Patients who do not complete a questionnaire will be excluded from the patient analyses. Results will be compared by Wilcoxon signed-rank test.

VII.d.iv Safety Analyses

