The participation of individual subjects in the study will be discontinued if:

- Subjects experience one episode of diabetic ketoacidosis (DKA) requiring hospitalization
 - Hyperglycemic events will be classified as DKA if the following are present:
 - Symptoms including but not limited to polyuria, polydipsia, nausea or vomiting
 - Serum ketones > 1.5 mmol/L or large/moderate urine ketones
 - Either arterial blood pH <7.30 or venous pH < 7.24, or serum bicarbonate < 15
 - Treatment provided in a healthcare facility
- Subjects experience one episode of severe hypoglycemia, defined as requiring the assistance of

another person due to altered consciousness, and required another person to actively administer carbohydrate, glucagon or other resuscitative actions. This means the participant was impaired cognitively to the point that he/she was unable to treat himself/herself, was unable to verbalize his/her needs, was incoherent, disoriented, and/or combative, or experienced seizure or coma. If plasma glucose measurements are not available during such an event, neurological recovery attributable to the restoration of plasma glucose to normal is sufficient evidence that the event was induced by a low plasma glucose concentration.

- Subjects experience persistent nausea and vomiting thought to be related to glucagon dosing in the bi-hormonal bionic pancreas arm
- The investigator believes it is unsafe for the participant to continue in the study
- A participant becomes pregnant
- The participant requests that the study be stopped

If more than 1 subject must be withdrawn from the study for severe hypoglycemia or DKA, the study will stop and a vote of the DSMB will be required to restart it. All serious and unexpected events will be reported to the DSMB within 72 hours.

Study participation is voluntary, and participants may withdraw at any time. The investigator may withdraw a participant who is not complying with the protocol. For participants who withdraw, their data will be used up until the time of withdrawal. For participants using the iLet who withdraw, a study provider will help them transition to their own therapy safely.

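### The primary endpoint never counts hours when the iLet is unpowered or absent because of a device fault as failure time, yet the same fault with the unit left on counts against success.

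*Combined protocol and SAP*

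**What the plan says.** Section II (Primary endpoint) and section VII.d.ii define operational success for each 7-day patient-period in matching terms. Three criteria must all hold "during the time that the iLet is powered on over the entire treatment period":

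- Criterion 1: valid CGM readings captured for at least 80% of the time.
- Criterion 2: each drug channel available for at least 95% of the time. Among other conditions, VII.d.ii requires "no pending occlusion alarm or other system failure to prevent attempting a delivery on that channel".
- Criterion 3: the ratio of delivered to attempted doses lies between 0.95 and 1.05. "Attempted doses refer to calculated doses that are issued for delivery when the channel is available".

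Neither section sets a minimum number of powered-on hours or says how fault-related power-off is scored. The result is reported as follows: "The proportion of patients that are operationally successful will be presented by pump type". Section VII.a says the endpoint shows whether the system works "with an acceptable degree of reliability and accuracy" and that it is not formally tested.

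Section VI.d.iii foresees technical faults, complete failure of the iLet with temporary return to usual care, and device replacement. It expects correction or replacement within 12 hours in most or almost all cases. Section VII.e.ii collects the time not under bionic pancreas control and a list of technical faults with cause and resolution.

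**The concern.** Section VII.b says that the study mainly serves to verify that the iLet operates as expected outside the clinic. Loss of the whole unit is the plainest failure to operate, and the protocol plans for it. Yet the success rule has no place for it. An hour with a blocked channel on a running unit is a failed hour, whereas an hour with a dead or removed unit is not scored at all.

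Two patients with the same fault could therefore be classified differently only because one unit was switched off. The reported proportion would then partly reflect how faults were handled and not only how reliably the device worked. With about 10 periods per configuration, a single reclassified period is visible in the result.

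**Working it through.** The plan gives no figure to reproduce: the sample size is a judgement and the primary endpoint has no test. The check is arithmetic on the scoring rule.

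**Inputs from the documents.** Period length 7 × 24 = 168 h (II). Thresholds 80% and 95% (II, VII.d.ii). A 12 h time for correction or replacement (VI.d.iii). Ten completing subjects (V.a, VII.b).

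**Assumption.** A fault leaves the unit off for some or all of the outage. The documents do not say whether it does, so the full range is shown. The 12 h is used as an illustrative outage length.

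**Tolerance.** Criterion 2 allows 0.05 × 168 = 8.4 h unavailable in a fully powered period. Criterion 1 allows 0.20 × 168 = 33.6 h without valid CGM.

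**Criterion 2, a 12 h fault, no other problem.** Let x be the hours of the fault during which the unit is on. As written, availability = 156/(156 + x).

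| Hours on (x) | Hours off | As written | Result | If fault-related off time is counted |
|---|---|---|---|---|
| 12 | 0 | 156/168 = 92.9% | fail | 92.9%, fail |
| 8 | 4 | 156/164 = 95.1% | pass | 92.9%, fail |
| 4 | 8 | 156/160 = 97.5% | pass | 92.9%, fail |
| 0 | 12 | 156/156 = 100% | pass | 92.9%, fail |

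The period passes when x ≤ 156/0.95 − 156 = 8.21 h, that is, once the unit is off for at least 12 − 8.21 = 3.79 h.

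**Shorter outages.** With h hours off, counting them changes a pass to a fail only if powered-on availability is at least 95% but below 0.95 × 168/(168 − h). For h = 4 that limit is 159.6/164 = 97.3%. An otherwise clean period with up to 8.4 h off passes either way.

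**Criterion 1.** A 12 h outage changes this criterion only if powered-on capture lies between 80% and 0.80 × 168/156 = 86.15%.

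**Criterion 3.** Doses are counted only when issued on an available channel, so off time does not enter. This criterion does not close the gap.

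**Effect of the shrinking denominator.** With 8 h of other unavailability and no outage, availability is 160/168 = 95.24% (pass). Add 12 h off and it is 148/156 = 94.87% (fail). Off time can thus lower a borderline score, but only because the other losses weigh more; the outage itself is still not counted.

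**Size in the reported result.** With 10 completers, one reclassified period moves that configuration's proportion by 1/10 = 10 percentage points.

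**The case against.** The strongest reply is that the powered-on condition is a choice of estimand. It appears in both sections, so it looks deliberate: the endpoint describes performance while the device runs, and an unpowered unit calculates no doses. This has force, and it is why the powered-on result should be kept. But VII.a claims reliability, and under the present rule the same fault can pass or fail depending on the power state. A choice of estimand does not by itself justify that.

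A second reply is that section VII.d.i already covers the matter: "Data from periods when the bionic pancreas was not in use will be included, if available". That is a general rule with a condition attached. The specific powered-on definition governs the primary endpoint.

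A third reply is that outages will be seen anyway. Largely true: off-control time and faults are collected, individual listings are planned, and X.b suspends the study for a recurring malfunction in several participants. None of these enters the proportion, which is the primary result.

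A reader might go further in three ways that the documents do not support:

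- That off time can never lower the score. It can in borderline cases, as shown above.
- That 12 h outages are to be expected. The figure is a time for correction or replacement, and no failure rate is given.
- That an arm cut short by a device fault will be scored a success. Sections VII.d.i ("In cases where an arm was not completed we will use the available data from that arm in the data analysis") and X.b ("For participants who withdraw, their data will be used up until the time of withdrawal") only imply scoring on observed time. Both definitions refer to a 7-day period, device fault is not a listed reason for individual discontinuation, and VI.d.iii provides for replacement.

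**Conclusion.** The gap in the scoring rule is certain from the text: fault-related hours with the unit off or absent are never themselves counted as failure time, while the same fault with the unit on counts against criterion 2. For a 12 h fault with no other problem, this is the difference between 92.9% (fail) and 100% (pass), with the change at about 3.8 h off.

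The practical consequence is less certain. It rests on the assumption that a faulty unit is off for part of the outage, and on an outage length that the documents do not predict. The effect is mainly on criterion 2 and narrow for criterion 1. No error rate or test decision is affected. What is affected is the meaning of the success proportion, in a study whose main purpose is to verify operation. It is worth correcting because the correction is cheap, not because the trial's results would otherwise be unusable.

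**What to change.** In sections II and VII.d.ii:

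1. For criteria 1 and 2, add to the denominator any time in the 7-day period when the iLet is unpowered or absent because of a documented device fault, including a shutdown prompted by a fault. Count it as CGM not captured and channel unavailable.
2. Leave out battery changes, permitted removal, shutdown not prompted by a fault, and withdrawal unrelated to the device.
3. Beside the proportion, report powered-on hours out of 168 h and fault-related off hours for each patient-period.
4. Keep the powered-on-only version as a supportive result.
5. Treat off time of undetermined cause as fault-related in a sensitivity analysis only. Battery changes are the subject's task under VI.d.iii, so an unexplained shutdown need not be a device failure.
6. State that an arm ended early because of a device fault is scored as not successful.

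Criterion 3 can stay as it is.

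The cost is a short scoring rule and the work of linking each off interval to a cause. The fault list in VII.e.ii supplies causes. The time not under bionic pancreas control is also collected, but it is not the same as powered-off time, because a subject may be disconnected with the unit on; the off intervals must be identified separately. The success proportion may come out less favourable. The rule should be fixed before results are known, so that no one has to decide afterwards how to score a dead unit.

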- Mean CGM glucose across days 2-7
- Proportion of time across days 2-7 within the CGM glucose range of 70-180 mg/dl
- Quality of life among study participants, their caregivers, partners and/or family members
- Treatment satisfaction among study participants, their caregivers, partners and/or family members

Safety endpoints

- Frequency of adverse events
- Frequency of severe hypoglycemia
- Frequency of diabetic ketoacidosis

Other endpoints

[figure not shown]
- Proportion of time across days 2-7 within each of the following CGM glucose ranges:
 - < 50 mg/dl
 - < 60 mg/dl
 - < 70 mg/dl
 - 70-120 mg/dl > 180 mg/dl
 - > 250 mg/dl
- Number of episodes of symptomatic hypoglycemia (reported daily by subjects)
- Percentage of subjects with mean Dexcom CGMG < 154 mg/dl (estimated average glucose corresponding to an A1c of 7%)
- MARD for the Dexcom G5 with the Contour Next One glucose meter as the reference
- Total daily dose of insulin
- Mean daily basal insulin dose
- Mean daily bolus insulin dose
- Total daily dose of glucagon
- Number of user-initiated glucagon doses
- Number of meal announcements
- Glucose variability measured with coefficient of variation (CV) and with mean of daily difference (MODD)
- Mean nausea severity from VAS
- Number of unscheduled insulin and glucagon cartridge/infusion set changes
- Mean glucose target

III. Study Design

III.a Overall Design

The study follows a 2-treatment, 2-period crossover design, 2 and will consist of two 7-day study arms in random order: one bihormonal bionic pancreas arm using insulin lispro or insulin aspart and dasiglucagon, and one insulin-only bionic pancreas arm using insulin lispro or insulin aspart, as seen in Figure 1.

Figure 7. Study design

Questionnaires will be administered to participants and their partners (designated contacts) at the beginning of the study and the end of each arm to gather data on attitudes towards bionic pancreas BG control, confidence, device burden and treatment satisfaction. This information will be used to make the best choices about how the final version of the bionic pancreas should be configured and used.

III.b Scientific Rationale for Study Design

A crossover study design was chosen to reduce the impact of inter-subject variability and to increase the statistical power to detect differences in secondary outcomes despite the relatively small number of subjects.

III.c End of Study Definition

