- Participants will be trained on the insertion and use of the Dexcom G5 CGM. Participants will insert their own CGM sensor and study staff will confirm they are doing it correctly.
- Study staff will review all study procedures and policies (including the use of the Dexcom G5, the Contour Next One, the Precision Xtra ketone meter, and the iLet device) and the upcoming visit schedule.
- The Dexcom G5 will be calibrated by the participant using the Ascensia Contour Next One SMBG glucometer, and study staff will confirm they are doing it properly.
- Participants will be trained on the use of the iLet.
- The control algorithm will be initialized with the participant's current weight
- The participant will remove his/her own insulin infusion pump and the participant will set up and start the iLet under the supervision of study staff. Participants will be instructed to not take any further insulin outside of the iLet throughout the study.
- The staff will confirm that the iLet is functioning properly prior to discharging the participant.
- All participants will be given Dexcom G5 CGM sensors, an Ascensia Contour Next One SMBG meter with test strips, ketone meter with strips, insulin, dasiglucagon for the bihormonal study arm, a glucagon emergency kit, an iLet, iLet pigtail adapters and Contact Detach infusion sets (an alternate infusion set may be supplied if the subject is known not to do well with the Contact Detach).

Day 7/Day 1 Visit:

- There may be no washout between the two study arms or the washout period may be up to 7 days.
- At the end of the first 7-day arm, subjects will return to the clinic and answer the post questionnaires for the study arm.
- The body weight, heart rate and blood pressure of the subject will be documented
- Blood will be drawn for a chemistry panel and complete blood count.
- Study staff will review any changes in the participant's medical history or medications to ensure continued eligibility, and any adverse events that may have occurred since their last study visit. Study staff will specifically ask subjects if they had any infusion site reactions or other skin irritation in the past 7 days, and will document any reactions.
- The iLet and the study glucometer will be downloaded. The memory of the iLet will be wiped and

it will be re-initialized for the next study period.

- Participants will replace their CGM sensor and calibrate when prompted if they haven't already.

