- Study staff will review all study procedures and policies (including the use of the Dexcom G5, the Contour Next One, and the iLet) and the upcoming visit schedule.
- The control algorithm will be initialized with the participant's current weight. The participant will set up and start the iLet under the supervision of study staff. Participants will be instructed to not take any further insulin outside of the iLet throughout the study.
- The staff will confirm that the iLet is functioning properly prior to discharging the participant.
- All participants will be given additional supplies as needed.

Final Day 7 Visit:

- At the end of the second 7-day arm, subjects will return to the clinic and answer the post questionnaires for the study arm.
- The body weight, heart rate and blood pressure of the subject will be documented.
- Blood will be drawn for a chemistry panel and complete blood count.
- An EKG will be performed. This EKG will be assessed relative to the baseline EKG to identify any potential changes.
- Any changes to medications or medical history and any adverse events that may have occurred since their last study visit will be documented. Study staff will specifically ask subjects if they had any infusion site reactions or other skin irritation in the past 7 days, and will document any reactions.
- The iLet and the study meters will be downloaded.
- All equipment will be collected and cleaned. The Dexcom G5 transmitter will be cleaned using the validated cleaning and disinfecting procedures.
- A study provider will review the last few hours of glucose trend data and insulin and dasiglucagon on board from the iLet, and assist the participants in resuming their usual diabetes management.

Follow Up Visits

- Subjects will return for a follow up visit 10 days (± 3 days) after the final day 7.
 - Any changes to medications or medical history and any adverse events that may have occurred since their last study visit will be documented. Study staff will specifically ask subjects if they had any infusion site reactions or other skin irritation since their last study visit, and will document any reactions.
 - Blood will be drawn for anti-drug antibodies.
 - If the EKG on the final Day 7 visit showed any changes relative to the baseline EKG, an additional EKG will be performed at this follow up visit.
- Subjects will return for a second follow up visit 25 days (± 4 days) after the final day 7.

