- CGMG (CGM glucose) every five minutes from the Dexcom CGM
- All fingerstick BG measurements taken by the subject (meter download)
- Average glucose target used
- Insulin total daily dose from bionic pancreas download
- Glucagon total daily dose from bionic pancreas download
- Timing of meal announcements and size of meals announced from bionic pancreas download
- Time subjects were not under bionic pancreas control
- List of technical faults associated with the bionic pancreas including cause and resolution
- Body weight after each study arm
- Blood pressure after each arm
- Heart rate after each arm
- Skin reactions, if any, after each arm
- EKG after completion of the second arm, and at the first follow up visit if applicable
- Information collected from the daily email survey:

- Number of reported hypoglycemic events requiring carbohydrate intervention
- Total grams of carbohydrates taken to treat hypoglycemia
- Number of severe hypoglycemic events (defined as subject required assistance to treat)
- Mean nausea severity from VAS
- Number of unscheduled insulin cartridge/infusion set changes
- Number of unscheduled glucagon cartridge/infusion set changes
- Alcohol use (mean drinks per day)
- Exercise duration and exposure (duration X intensity)
- Data from questionnaires about attitudes and expectations regarding the bionic pancreas at baseline and on day 7 of each arm.

VIII. Risks and Discomforts

Subjects may experience mild discomfort associated with the insertion of infusion sets and the Dexcom CGM sensor into the SC tissues. The risk of discomfort due to insertion of infusion sets and sensors may be greater than in their lives outside the trial because more infusion sets and sensors are required than are used in usual care.

There is a risk of hypoglycemia. This risk is expected to be less than the risk during the subjects' lives outside of the trial based on data from earlier trials. All of our previous studies have shown that hypoglycemia is significantly reduced in all configurations of the bionic pancreas when compared with usual care.

There is a risk of hyperglycemia. This risk is expected to be less than the risk during the subjects' lives outside of the trial based on data from earlier trials. All of our previous studies have shown that hyperglycemia is significantly reduced in all configurations of the bionic pancreas when compared with usual care.

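### After baseline, questionnaires are scheduled only at the end of each arm and analyzed in pairs under an unclear 4-day rule, so anyone who stops early falls out of the quality-of-life and satisfaction comparison

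*Combined protocol and SAP*

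**What the plan says.** **When forms are collected.** Section III.a states: "Questionnaires will be administered to participants and their partners (designated contacts) at the beginning of the study and the end of each arm". The visit procedures in VI.d.iv agree. For period 1: "At the end of the first 7-day arm, subjects will return to the clinic and answer the post questionnaires for the study arm". For period 2: "At the end of the second 7-day arm, subjects will return to the clinic and answer the post questionnaires for the study arm". The data list in VII.e.ii is narrower still: "Data from questionnaires about attitudes and expectations regarding the bionic pancreas at baseline and on day 7 of each arm". Section VI.d.i puts designated contacts on the same schedule, with an online option. No section lists a questionnaire at early discontinuation.

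**How they are analyzed.** Section VII.d.iii sets an exposure minimum, "All questionnaire data for patients who have completed a minimum of 4 days with a device will be included", and then a completeness rule, "Patients who do not complete a questionnaire will be excluded from the patient analyses". Arms are compared by the Wilcoxon signed-rank test.

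**The general principle.** Section VII.d.i promises an intention-to-treat analysis and adds: "In cases where an arm was not completed we will use the available data from that arm in the data analysis". Section X.b says that data from people who withdraw are used up to the point of withdrawal.

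**Who must stop.** One listed reason in X.b is specific to an arm: "Subjects experience persistent nausea and vomiting thought to be related to glucagon dosing in the bi-hormonal bionic pancreas arm". Severe hypoglycemia, and ketoacidosis that needs hospitalization, also end participation, in either arm (VI.d.v, VI.d.vi, X.b).

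**The concern.** Quality of life and treatment satisfaction are listed secondary endpoints and part of the secondary objective (section II). Section III.a says the questionnaire results will inform how the final device is set up and used. Whether people find the glucagon-containing configuration acceptable is central to that decision.

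The schedule, the 4-day minimum, the completed-form rule and the paired test all remove people who stop an arm early. Such people may well hold a different view of the arm they stopped. One route out, glucagon intolerance, exists in the bihormonal arm only. Early stops are also foreseen: section V.a allows up to 20 enrolled to reach 10 completers, partly because some experiments may end early. Replacing a stopper restores the number of pairs but not the missing opinion.

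**Working it through.** **1. Following an early stop through the rules.** Take a participant who stops the bihormonal arm early and whose participation then ends.

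| Stop | 4-day rule, per arm | 4-day rule, overall | Scheduled bihormonal form | Pair for the signed-rank test |
|---|---|---|---|---|
| After 2 days, period 1 | fails | fails (2 days) | none | none; insulin-only arm never started |
| After 5 days, period 1 | passes | passes | none | none; insulin-only arm never started |
| After 2 days, period 2 | fails | passes (7 + 2 = 9 days) | none | none |
| After 5 days, period 2 | passes | passes (7 + 5 = 12 days) | none | none |

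Both arms use the iLet, so the wording about days with a device does not settle which column applies. The last column is the same under either reading: with no form scheduled at the stop, no pair exists. Where site staff did obtain a form, the per-arm reading would still discard it after fewer than 4 days. That is hard to square with the available-data sentence in VII.d.i.

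**2. How likely is at least one early stop?** The documents give no rate, so this is an assumed range. With 10 starting, P = 1 − (1 − p)^10:

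- p = 2%: 18%
- p = 5%: 40%
- p = 10%: 65%
- p = 20%: 89%

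**3. Shift in the mean paired difference.** If k of N are missing and their mean difference is g standard deviations (SD) less favorable to bihormonal than the completers' mean, the completers-only mean is shifted by (k/N) × g. For g from 0.5 to 2 (assumed):

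- 1 of 10 missing: 0.05 to 0.20 SD
- 2 of 10 missing: 0.10 to 0.40 SD
- 3 of 10 missing: 0.15 to 0.60 SD
- 2 of 12 missing, with 10 completers reached by enrolling more: 0.08 to 0.33 SD

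If the missing people were instead dissatisfied with insulin-only, the shift has the opposite sign.

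**4. Sensitivity of the signed-rank test at this size.** These are exact two-sided p-values on assumed data.

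- Nine completers, all favoring bihormonal: 2 × 1/2^9 = 2/512 = 0.004.
- Add one stopper with the largest rank against bihormonal: the negative rank sum is 10. There are 43 subsets of the ranks 1 to 10 with sum at most 10, so p = 2 × 43/1024 = 0.084.
- A less uniform pattern, with eight of nine favoring bihormonal and the smallest rank negative: p = 0.008. With 1, 2 or 3 worst-ranked stoppers added, p = 0.11, 0.37 and 0.73.

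The plan gives no figure of its own to reproduce. The 10 subjects in VII.b rest on judgment, with no effect size, SD or dropout rate.

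**The case against.** **The end of an arm need not mean day 7.** Section III.a refers to the end of each arm, and a 4-day minimum would have little purpose unless shortened arms could yield forms. That is a fair reading of intent. But VII.e.ii names day 7, both visit descriptions refer to a completed 7-day arm, and no early-stop form is listed. What stands is that the documents do not schedule one, not that none could ever be obtained.

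**The direction is not fixed.** A reader might infer that the comparison must favor bihormonal. The documents do not support that. Severe hypoglycemia and ketoacidosis stops apply to both arms. Insulin-only runs here at 110 mg/dl, the lowest target allowed in that mode. In the earlier unmonitored comparison (section I.e), hypoglycemia was 1.66% on insulin-only and 0.99% on bihormonal, although bihormonal then ran at 100 mg/dl. Section VIII describes nausea and vomiting as infrequent in past studies. Stops could therefore also remove people unhappy with insulin-only. This objection stands.

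**A reader might also infer that one exclusion overturns the result.** It does not. In the illustration nine of ten still favor bihormonal, and VII.d.i treats p-values as an aid to interpretation, without formal superiority testing. The weaker point survives, because descriptive means, medians and differences come from the same selected people.

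**An early form alone is not enough.** A period 1 stop leaves no second-arm score, so the form cannot enter a paired test. This is correct, and the fix has to allow for it.

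**Early stops will be visible anyway.** Discontinuation reasons, adverse events by treatment, individual listings and daily nausea scores are all planned (VII.d.iv, VII.d.v, VII.d.viii, VII.e.ii). This limits the harm but does not supply the missing quality-of-life and satisfaction scores.

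**Conclusion.** The point holds in conditional form. If early stops occur, the questionnaire comparison is restricted to people who tolerated the arms, contrary to the intention-to-treat and available-data statements in VII.d.i. The 4-day rule is also ambiguous between a per-arm and an overall count. Stops for glucagon-related nausea and vomiting would tend to flatter the bihormonal arm; other mandated stops could act in either direction. Neither the net direction nor the size can be derived from the documents.

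On the assumed inputs, one missing person in ten moves the mean difference by 0.05 to 0.20 SD, and one worst-ranked stopper moves the illustrative p from 0.004 to 0.084. Both show sensitivity at n of about 10; neither is a forecast.

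The weight is moderate. These are secondary endpoints in a small study whose main purpose is to verify device operation, but the affected results are meant to inform the final device and the remedy is cheap.

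**What to change.** - **Collection.** In VI.d.iv and VII.e.ii, schedule the post-arm questionnaire whenever an arm is stopped, whatever the day, for participants and designated contacts. Allow online completion; participants already fill in a daily web survey (VI.d.iii) and contacts may already respond online.
- **Main summary.** In VII.d.iii, include every available form, summarized by arm, and keep the paired comparison for those with both forms. This brings the section into line with VII.d.i.
- **4-day rule.** State that it applies per arm, and use it only as a sensitivity analysis.
- **Reporting.** Tabulate missing forms by arm, period and reason.
- **Worst-rank sensitivity analysis.** For treatment-related stops that leave no usable pair, assign the worst rank against the arm that was stopped. Include period 1 stops where the second arm was never started. Label it as a bounding analysis, since it assumes a preference over an arm the person may not have used.

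The cost is revised wording, one extra form trigger and a short table. The downside is that scores after only 1–3 days of use are noisier; the per-arm 4-day sensitivity analysis shows how much that matters.
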